6.4. Baseline covariates

The following is a description of the baseline covariates that will be used in the various analyses outlined in the remainder of Section 6.

- Stratifying variables
 - serum uric acid (sUA) at baseline with 2 levels (≤ 6.0 and > 6.0 mg/dl)
 - glycated hemoglobin (HbA1c) at baseline with two levels (≤ 7.8 and $> 7.8\%$)
 - clinical site/study center with 16 levels (based on main sites with satellite sites collapsed into main sites)
- Baseline iGFR measured at Visit 4
- Baseline eGFR measured at Visit 4
- Treatment group with two levels (Allopurinol, Placebo)
- Albuminuria status with 2 levels (subjects who qualified by ACR or AER or were albuminuric at baseline vs. subjects who qualified by eGFR slope and were normoalbuminuric at baseline)
- Baseline AER geometric mean (at Visits 3 and 4 combined) expressed on log to base 10 scale

As of Dec. 17, 2018, we have complete data available for baseline serum uric acid, treatment group, and study center. The number of missing values for the other baseline covariates is 1 for iGFR, 2 for HbA1c, and 17 for albuminuria status. Missing baseline data will be imputed according to the approach described in Section 6.5. When creating covariates for analytical and imputation purposes, we will aggregate clinical sites with a small number of randomized subjects, such as Edmonton (site #11, n=3) and Vancouver (site #16, n=11) will be combined with Calgary (site #10, n=20) in the same geographic region. Similarly, Spokane (site #15, n=5) will be combined with Seattle (site #13, n=35).

6.5. Missing values

Missing values both for baseline characteristics and for outcomes/endpoints of interest are inevitable, especially in studies with longer follow-up. To effectively address missing values that occurred for baseline covariates and for post-randomization variables of interest, and the necessity to consider post-ESRD iGFR values as an unfavorable outcome, models involving direct likelihood methods are difficult to implement. For this reason, we will perform the analyses using a *multiple imputation* (MI) approach consisting of three steps:

Step 1. Using an *imputation* model, create multiple datasets with missing values imputed

Step 2. Fit *substantive models* described in Sections 6.6 and 6.7 using imputed datasets created in Step 1

Step 3. For each substantive model, combine the results obtained in Step 2 for the inference using Rubin's rule (Rubin, 1987).

To create imputed datasets in Step 1, we will employ multivariate imputation by means of fully conditional specification (FCS) method introduced by van Buuren et al, 2006. This method is especially attractive in our case because it handles non-monotone patterns of missingness, and arbitrary types of imputed variables, i.e. both continuous and categorical. The imputation model will include baseline covariates listed in Section 6.4. In addition, to make imputation model more general than substantive models, we will include HbA1c at Visit 1 and geometric mean of AER at Visit 3 and 4 expressed on logarithmic base to 10 scale predictive of other baseline covariates.

We will also include eGFR at all post-randomization visits, i.e., Visit 6-17, iGFR at Visits 11, 16 and 17, AER at Visits 15, 16 and 17 expressed on logarithmic base to 10 scale. Imputation of baseline variables will be performed starting with variables having the lowest number of missing values. Variables measured longitudinally, i.e., eGFR and iGFR, will also be modeled sequentially in order determined by visit number. To preserve different response patterns in the study treatment groups (i.e., treatment group by study visit interaction) imputations will be performed separately in each group. Resulting data will consist of 25 imputed datasets. We note that the FCS method imputes data under the missing at random (MAR) assumption, e.g., the probability that the iGFR/eGFR value is missing depends on *observed* rather than *unobserved* values of the variable. Although we consider the MAR assumption to be sensible for our study, it does not apply for post-ESRD iGFR/eGFR values. To model *post-ESRD eGFR* measures as a deviation from the MAR assumption, we will impute these values using a controlled imputation technique, specifically the delta-adjustment approach (O’Kelly, Ratitch, 2014). This technique will impute post-ESRD eGFR values on average at 7 ml/min/1.73m², with a small variation around it, that is consistent with: (1) attributing to missing post-ESRD eGFR values the value representing ‘the worst case scenario’, (2) assigning a biologically acceptable value, and (3) including the ‘absorbing state’ feature of ESRD. We note that eGFR measures are taken at every visit and are used to determine time of developing ESRD. For this reason pre-ESRD eGFR values are highly predictive of post-ESRD iGFR values. In addition, we note that post-ESRD iGFR and eGFR values lie in a very narrow range and they are effectively interchangeable. For these reasons, we will impute post-ESRD iGFR values by using corresponding post-ESRD eGFR imputed values as a proxy. We note that the imputation of *eGFR* and *iGFR* values for subjects who *did not develop* ESRD and have low values to start with may lead to imputed values lower than 15 ml/min/1.73m², which is biologically implausible. For this reason, imputed values of *eGFR* and *iGFR* for subjects who *did not develop* ESRD will be truncated at 15 ml/min/1.73m². Similarly, log(AER) base 10 imputed values for these subjects will be truncated at a lower limit of detection of -0.60206 (= log₁₀(0.25)).

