5.4. Randomization Procedures

After the run-in period (described in Section 8.3) and with a valid baseline iohexol GFR measurement prior to randomization, participants will be randomized in a 1 to 1 ratio to receive either oral allopurinol or placebo. Randomization will be stratified by center, uric acid (≤ 6.0 vs. > 6.0 mg/dl), and HbA1c (≤ 7.8 vs. $> 7.8\%$). Randomization will be performed using permuted blocks, with a block size that is known only to the DCC. After a participant has been randomized, the clinical site will send a study medication request to the research pharmacy, including the participant's address, so that the study medication can be directly mailed to the participant. Clinical sites will not have access to the treatment

assignment (see 6.2., Blinding Procedures). This will be directly communicated or made electronically available to the pharmacy by the DCC.

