11.10. Sample Size

Since a variance-covariance matrix for the iGFR measures is not available and this matrix is essential in order to perform formal power calculations for a model with correlated errors, we performed alternative power calculations based on an intent-to-treat analysis within an ANCOVA framework. Specifically, we assumed that the primary hypothesis is tested in the following model:

$$M1: \text{iGFR at washout} = \text{iGFR at baseline} + \text{treatment group}$$

Compared to the model that will be used in the primary analysis, model M1 is simplified in two aspects. First, it does not use information from iGFR values measured at intermediate time points. Second, it does not include covariates such as the stratifying variables (HbA1c and UA) or other GFR predictors such as baseline AER. Both of these aspects may lead to loss of precision of the treatment effect estimate. Consequently, our sample size calculations should be considered as conservative.

The hypothesis being tested, i.e. the effect of treatment on iGFR at washout, corresponds to testing whether the treatment group factor in Model M1 is significant. The choice of the ANCOVA model for the purpose of power calculations is sensible, as residuals from a univariate model involving baseline iGFR as covariate fitted to data from RASS study conform to normal distribution. Sample size calculations were performed based on Cohen⁴⁵ and making the following assumptions:

1. Postulated effect on iGFR at washout (\cdot) = 3 ml/min/1.73 m². We deem this effect to be clinically meaningful and attainable. It is clinically meaningful because it would translate on average into a 10-year delay in the progression to ESRD. It is attainable because it is smaller than the difference in 3-year GFR that we observed in the JKS between subjects with serum UA \geq 4.5 mg/dl compared to those with levels below this value. The postulated effect was based on the following changes in GFR levels in the two treatment groups:

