 - a. Untreated group = 3 ml/min/1.73 m² per year. This estimate is based on data from the Joslin Kidney Study (JKS), in which the median GFR loss among 43 subjects meeting the above criteria was 3.1 ml/min/1.73 m² per year, with 70% of subjects having a GFR loss $>$ 1.5 ml/min/1.73 m² per year. Also, among 116 subjects from Steno who met the albuminuria and GFR criteria, but for whom serum uric acid values were not available, the median GFR loss was 3.3 ml/min/1.73 m² per year, with 71% of subjects having a GFR loss $>$ 1.5 ml/min/1.73 m² per year.
 - b. Treated group = 2 ml/min/1.73 m² per year. The average GFR loss in the JKS subjects with serum UA $<$ 4.5 mg/dl was 1.5 ml/min per year. On this basis, we conservatively assumed that the allopurinol treatment, if effective, would decrease the GFR loss to 2 ml/min per year (a 33% decrease compared to the untreated group).

2. Standard deviation (SD) of residual error = 10.1 ml/min/1.73 m². This was estimated based on the root-mean-squared error from a regression model with eGFR at 3 yrs as the dependent variable and baseline eGFR as the independent variable fitted to data concerning T1D patients from the Joslin Kidney Study meeting the PERL inclusion criteria.

Assuming a two-sided alpha error equal to 0.05, the effective sample size needed to detect the pre-specified treatment effect ($\delta = 3$ ml/min/1.73 m²) at washout adjusted for baseline iGFR with 80% power is equal to n=180 per group. To take into account the anticipated overall dropout rate (up to 5%/yr or 15% over the entire duration of the study) and drug discontinuation or non-compliance in the treatment group (up to 2%/yr or 6% over the entire duration of the study), and to maintain the desired

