6.8. Other analyses

6.8.1. Subgroup analyses

To investigate the possible presence of heterogeneity in the response to allopurinol, subgroup analyses (based on the primary efficacy analysis described in subsection 6.6.1, with the inclusion of appropriate interaction terms with the subgroup variable) will be performed by age groups (≤ 50 and > 50 yrs), gender, racial/ethnic group, HbA1c (≤ 7.8 and $> 7.8\%$), serum uric acid (≤ 6.0 and > 6.0 mg/dl), baseline iGFR (≤ 60 ml/min and > 60 ml/min/1.73m²), AER at baseline (≤ 50 and > 50 mg/24 hr), and albuminuria status (subjects who qualified by ACR or AER or were albuminuric at baseline vs. subjects who did qualify by eGFR slope and were normoalbuminuric at baseline).

An example of such subgroup analysis for age groups (≤ 50 and > 50 yrs) is provided below. Similar to Equation (6.1) for each time t ($t = 1, 2, 3$), corresponding to visits V11, V16, V17, we specify the model:

$$iGFR_{it} = \beta_{0t} + \beta_{1t} TRT_i + \beta_{2t} AGE_i + \beta_{3t} AGE_i \times TRT_i + \mathbf{x}'_i \boldsymbol{\beta} + \epsilon_{it}, \quad (6.2)$$

where $iGFR_{it}$ is the value of iGFR at time t for subject i ($i = 1, \dots, 530$). Fixed effects $\beta_{0t}, \beta_{1t}, \beta_{2t}, \beta_{3t}$ for $t = 1, 2, 3$ denote visit-specific intercepts, treatment effects, age effects and age by treatment interactions, respectively. TRT_i is treatment group (equal to 1 for the allopurinol and 0 for placebo). AGE_i indicates age group (≤ 50 and > 50 yrs). Stratifying variables, and baseline covariates albuminuria status, AER, iGFR for subject i are included in a vector of covariates \mathbf{x}_i and associated fixed effects are stored in vector $\boldsymbol{\beta}$. We assume that residual errors ϵ_{it} ($t = 1, 2, 3$) for subject i are normally distributed with zero mean and 3x3 general/unstructured variance-covariance matrix. The model specified in (6.2) will yield the estimates of visit-specific treatment by age interaction effects $\beta_{31}, \beta_{32}, \beta_{33}$ for all three visits V11, V16 and V17. In the context of subgroup analysis, we are interested in β_{33} , which represents treatment by age interaction at Visit 17 adjusted for baseline covariates.

Analysis	Subgroup Analysis of the Primary Endpoint: iGFR at the end of the 2-month wash-out period (Visit 17) by Age group
Analysis Set	ITT Population
Methods	Linear model for repeated measures with correlated errors

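### The SAP 6.5 imputation model omits age, gender and racial/ethnic group; if the 6.8.1 subgroup models use the imputed data, these three treatment interactions are pulled modestly toward zero

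*SAP*

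**What the plan says.** SAP 6.5: "The imputation model will include baseline covariates listed in Section 6.4". The 6.4 list holds serum uric acid, HbA1c, site, baseline iGFR, baseline eGFR, treatment, albuminuria status and log10 AER. Section 6.5 then adds HbA1c at Visit 1 and AER at Visits 3 and 4, "to make imputation model more general than substantive models". It also adds eGFR at Visits 6 to 17, iGFR at Visits 11, 16 and 17, and AER at Visits 15 to 17. Imputation is run separately in each arm. Age, gender and race appear nowhere.

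SAP 6.8.1 tests a treatment-by-subgroup interaction at Visit 17 for eight variables: age group, then "gender, racial/ethnic group, HbA1c", serum uric acid, baseline iGFR, AER and albuminuria status. It bases the model on 6.6.1, the primary analysis, which is carried out under multiple imputation. Protocol 11.7 classes the subgroup analyses as strictly exploratory.

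**The concern.** If a subgroup variable is absent from the imputation model, an imputed Visit 17 value within an arm depends on that variable only through the participant's own earlier measurements. Among participants with imputed values, the treatment difference therefore varies less across the subgroup than it really does. Pooling them with the observed participants shrinks the interaction.

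What is at stake is under-reported heterogeneity by age, gender or race, in tests that have little power to begin with. SAP 3.3 moved the age cut-point from 40 to 50 years to balance the groups, so the sponsor wants this analysis to be informative. The tipping-point analysis in 6.6.1 shifts Visit 17 values in the allopurinol arm and does not address this problem.

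**Working it through.** **1. The plan's own figure.** The inputs are in Protocol 5.4 and 11.10: "participants will be randomized in a 1 to 1 ratio"; "Assuming a two-sided alpha error equal to 0.05"; "Postulated effect on iGFR at washout" of 3 ml/min/1.73 m²; "Standard deviation (SD) of residual error = 10.1"; and "with 80% power is equal to n=180 per group".

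n per arm = 2 × [10.1 × (1.960 + 0.842) / 3]² = 177.9, so 178, against the stated 180. The Model M1 column of Table 1 also reproduces. With 15% dropout, 240 × 0.85 = 204 per arm and the standard error is 10.1 × √(2/204) = 1.00. Power is then 0.851 with no non-compliance, and 0.805 with the effect cut by 6% to 2.82. The table gives .85 and .80. The plan gives no figure for the dilution itself.

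**2. Bound.** Let m be the missing Visit 17 share and λ the part of the interaction that a participant's earlier measurements carry into the imputed value. Then

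retained share = (1 − m) + mλ = 1 − m(1 − λ).

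With no follow-up data, λ = 0 and the retained share is 1 − m, which is 0.85 at m = 0.15.

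**3. Simulation of λ.** There were 400,000 simulated subjects, with sequential regression imputation within each arm and the interaction estimated at Visit 17. These assumptions are not in the documents: a 50/50 binary subgroup; an interaction growing linearly in time; Visit 17 SD given baseline of about 9; dropout unrelated to outcome. The interaction retained with the subgroup variable left out was:

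| Missing at Visit 17 | All dropout before first follow-up | Spread over visits | Only Visit 17 missing |
|---|---|---|---|
| 9% | 0.91 | 0.93 | 0.98 |
| 15% | 0.84 | 0.90 | 0.97 |
| 20% | 0.80 | 0.87 | 0.96 |

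The 0.84 (0.844 unrounded) against the bound of 0.85 is simulation error. With the subgroup variable added to the by-arm imputation model, the retained share was 0.99 to 1.01 in every cell. A second, smaller simulation (250 trials, true interaction 4, 15% dropout spread over visits) gave 3.57 without age and 4.00 with it, against 4.01 in the full data: 3.57 / 4.01 = 0.89.

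**4. Scale.** With N = 530 (SAP Section 1) in four equal cells of 132.5, the interaction standard error is 10.1 × √(4/132.5) = 1.76. For an interaction of 3 ml/min, a 10% loss is 0.3 ml/min, or 0.3 / 1.76 = 0.17 standard errors. A 16% loss is 0.48 ml/min, or 0.27 standard errors. Holding the standard error fixed, power for that interaction falls from 0.40 to 0.34 at a retained share of 0.91, and to 0.31 at 0.85.

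**5. Does 6.8.1 use the imputed data?** Four things in the SAP point that way:

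- 6.8.1 is built on 6.6.1, which is run under multiple imputation.
- 6.8.2 and 6.8.3 expressly rule imputation out, and 6.8.1 does not.
- Equation 6.2 runs over all 530 subjects, as Equation 6.1 does.
- The reasons 6.5 gives for imputing (missing baseline covariates and iGFR after ESRD) apply equally to 6.8.1. Its model keeps albuminuria status (17 missing), HbA1c (2) and baseline iGFR (1).

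**The case against.** The strongest objection is that the SAP never says 6.8.1 is fitted to the imputed datasets. Step 2 of 6.5 names only Sections 6.6 and 6.7 as the models to be fitted to them. The 6.8.1 Methods row repeats the wording of the 6.6.1 row without the reference to multiple imputation, and 6.1 also allows methods that handle missing outcomes directly. A likelihood fit to observed iGFR would not produce this dilution. That stands: the bias is conditional. The Methods row is weak evidence, though. The 2017 SAP used the same words for its subgroup analysis when its primary outcome was not multiply imputed either, so the row may simply have been carried over.

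A reader might infer three stronger things that the documents do not support.

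- *That 6.5 contradicts its own aim of generality.* Step 2 ties the substantive models to Sections 6.6 and 6.7, and none of those models uses age, gender or race. For them the aim is met.
- *That all the subgroup interactions are diluted.* Five of the eight variables are already in the by-arm imputation model, which preserves their interactions (linearly, for baseline iGFR and AER).
- *That imputed values are drawn as if treatment worked equally across the three groups.* Imputation conditions on serial eGFR and iGFR, which carry part of the subgroup response. When only Visit 17 is missing, 0.97 of the interaction survives at 15% missing.

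The size is also uncertain. The 15% is an upper planning figure for dropout, and the SAP widens the iGFR windows to keep values in. The simulations use one binary subgroup; race is unlikely to split evenly, and the SAP defines no race levels.

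**Conclusion.** The omission is certain, and so is the direction of bias if 6.8.1 uses the imputed datasets, which is the more natural reading. On that reading, the age, gender and race interactions shrink toward zero by at most roughly the missing Visit 17 share: about 10% if dropout is spread over visits, with a range of 3% to 16%, at an assumed 15% missing. These figures rest on the simulation assumptions above and on a missing share that the documents do not report.

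The loss is small beside sampling error, but it is systematic and favors a finding of homogeneity. It does not touch the primary Visit 17 effect or the Section 6.7 results, and it concerns exploratory analyses only. It is worth correcting because the correction is nearly free.

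**What to change.** In SAP 6.5, add age (or the 6.8.1 age group), gender and racial/ethnic group to the by-arm imputation model. Collapse sparse race categories, as 6.4 already does for small sites. Because imputation is run separately by arm, adding the variables preserves their interaction with treatment. The age group itself is the better choice, since it is the form that 6.8.1 tests.

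In 6.8.1, state that the imputed datasets are used. If they are not meant to be used, say so, and state how missing baseline covariates and iGFR after ESRD are handled, since the subgroup analysis would then differ from the primary analysis on both.

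The cost is a few lines of SAP text and no new data collection. The downside is a slightly larger imputation model, with some risk of sparse race cells within an arm.

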6.6. Analysis for the primary estimand

In this Section we describe primary and secondary analyses aligned with the primary estimand defined in Section 5.1. These models will be employed as substantive models (see Step 2 of multiple imputation approach described in Section 6.5).

6.6.1. Primary analysis for the primary estimand

The goal of the primary analysis for the primary estimand is to test the null hypothesis of the difference in means between treatment arms in the primary endpoint (iGFR at the end of the 2-month wash-out period [Visit 17] following the 3-year intervention) being equal to zero. The analysis will be performed in a multiple imputation framework on the intention-to-treat (ITT) population and will employ a linear model for correlated errors with general/unstructured covariance matrix (Molenberghs and Verbeke, 2005; [name] and Burzykowski, 2013) as a substantive model. For each time t ($t = 1, 2, 3$) corresponding to post-randomization iGFR visits, i.e. visits V11 (80 weeks), V16 (156 weeks), and V17 (164 weeks after randomization) the model equation is specified as:

$$iGFR_{it} = \beta_{0t} + \beta_{1t} TRT_i + \mathbf{x}'_i \boldsymbol{\beta} + \epsilon_{it}, \quad (6.1)$$

where $iGFR_{it}$ is the value of iGFR at time t for subject i ($i = 1, \dots, 530$). Fixed effects β_{0t}, β_{1t} for $t = 1, 2, 3$ denote visit-specific intercepts and treatment effects. TRT_i is

treatment group (equal to 1 for the allopurinol and 0 for placebo). Stratifying variables (serum uric acid, HbA1c, study center), and baseline covariates: albuminuria status, AER, iGFR for subject i are included in a vector \mathbf{x}_i of p covariates (x_1, \dots, x_p) and associated fixed effects are stored in vector $\boldsymbol{\beta} = (\beta_1, \dots, \beta_p)$. We assume that residual errors ϵ_{it} ($t = 1, 2, 3$) for subject i are normally distributed with zero mean and 3×3 general/unstructured variance-covariance matrix. The model specified in (6.1) will yield the estimates of visit-specific treatment effects $\beta_{11}, \beta_{12}, \beta_{13}$ for all three visits V11, V16 and V17. In the context of the primary analysis of the primary endpoint, we are interested in parameter β_{13} , representing treatment effect at Visit 17 adjusted for stratifying variables and baseline covariates. The Kenward-Roger approximation will be used to estimate denominator degrees of freedom.

Estimand	Primary estimand defined in Section 5.2.1
Analysis	Primary Analysis of the Primary Endpoint: iGFR at the end of the 2-month wash-out period (Visit 17)
Analysis Set	ITT Population
Methods	Linear model for repeated measures with correlated errors using multiple imputation technique.
Dependent Variable	iGFR measured at Visits V11 (80 weeks) , V16 (156 weeks) and V17 (164 weeks after randomization)
Model	Fixed effects: 
 • Visit-specific intercepts corresponding to V11, V16, V17 • Visit-specific treatment effects corresponding to V11, V16, V17 • Stratifying variables: sUA, HbA1c, study center • Albuminuria status with 2 levels • Baseline AER geometric mean (at Visits 3 and 4 combined) expressed on log to base 10 scale • Baseline iGFR
Results	
 • Least square iGFR means at Visit 17 by treatment group. • Estimate of treatment effect at Visit 17 adjusted for baseline covariates • 95% confidence interval for treatment effect • P-value for treatment effect

We will assess the impact of deviation from the MAR assumption on the robustness of the results through a *sensitivity analysis*. For the primary estimand, it will be performed within the same multiple imputation framework; however we will employ marginal delta-adjusted method and apply it to Visit 17 with adjustments in allopurinol arm increasing by one unit of iGFR value until the MAR results are overturned, that is, we will use so called tipping point approach (O’Kelly, Ratitch, 2014).

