11.3. Primary Efficacy Analysis

For the primary endpoint (iGFR at the end of the 2-month wash-out period following the 3-year intervention), we will follow the recommendations by Carpenter et al^{38,39} and perform the analysis by means of a linear model for correlated errors with general/unstructured covariance matrix using all available iGFR measures (including those at baseline, 80, 156, and 164 weeks, respectively) as the dependent variable. By conditioning on the baseline iGFR measure we will also effectively use this variable as a covariate. Treatment group, study center, stratifying variables, albuminuria status (subjects who qualified by ACR or AER or were albuminuric at baseline vs. subjects who did not qualify by eGFR slope and were normoalbuminuric at baseline), baseline AER, time, and time by treatment interaction will also be included as covariates in the model. Three features make this analytical approach especially attractive:

1. If there is no dropout (a very unlikely case), the estimate of the treatment effect at the end of the 2-month wash-out period following the 3-year intervention and its precision obtained using this approach will be exactly the same as those based on a classical approach employing an analysis of covariance (ANCOVA) model with treatment group, study center, iGFR and AER/ACR measured at baseline included as covariates.
2. If the iGFR measure at the end of the wash-out period is missing, we will be able to efficiently use the information contained in the intermediate iGFR measurements obtained at 80 and 156 weeks, by virtue of them being correlated with the GFR measurement at washout. Estimate of the treatment effect obtained this way is valid under the missing at random (MAR) assumption. This is in contrast to the ANCOVA approach, which would lead to the loss of this information and would require a more stringent assumption about the mechanism of data missingness, i.e. a missing completely at random (MCAR) mechanism.
3. The underlying analytical framework allows the use of all post-randomization data and is well suited to investigate the reason for withdrawal, for example to study whether participants having low iGFR values are more likely to withdraw.

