3.2. Simplified model for the primary efficacy analysis using a multiple imputation approach

RATIONALE:

The primary efficacy analysis presented in Section 11.3 of the study protocol was based on a linear model for correlated errors using all available iGFR measures (including those at baseline, 80, 156, and 164 weeks, respectively) as the dependent variable.

To effectively address missing values in baseline covariates and the need to consider iGFR values that were not measured after end stage renal disease (ESRD) as an unfavorable outcome, direct likelihood based methods are difficult to implement. For this reason, we have decided to perform the primary efficacy analysis using a *multiple imputation* (MI) approach. To perform the MI analysis, we define both *imputation* and *substantive* models. We note that in the substantive model, iGFR at baseline is no longer included as a dependent variable.

PROTOCOL:

We specify the model as follows “... perform the analysis by means of a linear model for correlated errors with general/unstructured covariance matrix using all available iGFR measures (including those at baseline, 80, 156, and 164 weeks, respectively) as the dependent variable.”

SAP:

We specify the model as follows “... perform the analysis using a *multiple imputation* approach with a substantive model defined by means of a linear model for correlated errors with general/unstructured covariance matrix using all post-baseline iGFR measures (including those at 80, 156, and 164 weeks, respectively) as the dependent variable.

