Model	Fixed effects associated with: 
 • Visit-specific intercepts corresponding to V11, V16, V17 • Visit-specific effects of sUA change on iGFR at V11, V16, V17 • Stratifying variables: sUA, HbA1c, study center • Albuminuria status at baseline with 2 levels • Baseline AER geometric mean (at Visits 3 and 4 combined) expressed on log to base 10 scale • Baseline iGFR
Results	
 • Estimate of an effect of an average sUA changes from baseline on iGFR value at Visit 17, adjusted for stratifying variables and baseline covariates • 95% confidence interval for sUA changes effect • P-value for sUA changes effect

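### Equation 6.1 holds the baseline iGFR slope equal at weeks 80, 156 and 164; letting it vary by visit would protect the precision of the Visit 17 treatment effect at almost no cost

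*SAP*

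**What the plan says.** SAP 6.6.1 will "employ a linear model for correlated errors with general/unstructured covariance matrix" for iGFR at Visits 11, 16 and 17. The coefficients with a visit index t are those that "denote visit-specific intercepts and treatment effects". The covariates (sUA, HbA1c, center, albuminuria status, log10 AER, baseline iGFR) enter through one vector β without an index. The model table agrees: it lists "Visit-specific treatment effects corresponding to V11, V16, V17" and visit-specific intercepts, then the covariates with no such label. This is not loose notation. In SAP 6.8.4, where a covariate is meant to act differently by visit, the table says so: "Visit-specific effects of sUA change on iGFR at V11, V16, V17". Equation 6.2 likewise gives the subgroup variable a visit-indexed coefficient.

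Protocol 11.3 describes a different model, with baseline iGFR as one of the responses and an unstructured covariance matrix: "By conditioning on the baseline iGFR measure we will also effectively use this variable as a covariate". It adds that, without dropout, the estimate and its precision "will be exactly the same as those based on a classical approach employing an analysis of covariance (ANCOVA) model". SAP 3.2 replaces that model and states that "iGFR at baseline is no longer included as a dependent variable". It does not mention the consequence for the baseline slope.

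**The concern.** With baseline among the responses and an unstructured covariance, the slope of iGFR at visit t on baseline is cov(visit t, baseline) / var(baseline), which is free to differ by visit. Once baseline becomes a covariate with a single coefficient, the slope must be the same at all three visits.

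The slope may well change over 84 weeks, for instance if the correlation with baseline weakens with time. The common slope is then a weighted compromise, and most of the weight can fall on Visit 11, where residual variance is likely to be smallest. The part of baseline iGFR that is wrongly adjusted at Visit 17 stays in the Visit 17 residual. What is at stake is the standard error of the primary comparison, and so some power. Because baseline is balanced by randomization, the expected treatment effect is not at stake.

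**Working it through.** **1. The plan's own figure.** Protocol 11.10 gives a difference of 3, residual SD 10.1, two-sided α 0.05 and power 80%. n per group = 2(1.960 + 0.842)² × 10.1² / 3² = 178, against 180 stated. Inflation: 180 / 0.85 / 0.94² = 239.7, against 240 stated. These reproduce.

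**2. Variance of baseline iGFR.** Protocol 11.10 equates 10% of residual variance with 4% of total variance, so residual variance is 40% of the total and R² on baseline is 0.60. Total SD = 10.1 / √0.40 = 15.97. If the baseline SD equals this, the Visit 17 slope is √0.60 = 0.775.

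**3. Large-sample formula.** Let g be the common slope minus the Visit 17 slope. Then

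SE ratio = √(1 + g² × 15.97² / 10.1²) = √(1 + 2.5 g²).

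Assumptions not in the documents: residual SDs 7.5, 9.8 and 10.1 at Visits 11, 16 and 17; correlations 0.70 (V11, V16), 0.68 (V11, V17) and 0.85 (V16, V17). With these, the weights on the three visits in the common slope are about 0.89, 0.07 and 0.04.

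| Slopes V11 / V16 / V17 | V11 minus V17 | Common slope | g | SE ratio, formula | Simulated SE ratio, Eq. 6.1 to ANCOVA |
|---|---|---|---|---|---|
| 0.775 / 0.775 / 0.775 | 0 | 0.775 | 0 | 1.000 | 0.992 |
| 0.85 / 0.79 / 0.775 | 0.075 | 0.843 | 0.068 | 1.006 | 0.998 |
| 0.90 / 0.79 / 0.775 | 0.125 | 0.887 | 0.112 | 1.016 | 1.014 |
| 0.95 / 0.79 / 0.775 | 0.175 | 0.932 | 0.157 | 1.030 | 1.031 |
| 1.00 / 0.80 / 0.775 | 0.225 | 0.977 | 0.202 | 1.050 | 1.039 |

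Example for the last row: 0.89 × 1.00 + 0.07 × 0.80 + 0.04 × 0.775 = 0.977; g = 0.202; √(1 + 2.5 × 0.0408) = 1.050.

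The last column comes from 3,000 simulated complete-data trials per row, N = 530, with 14 null covariates standing in for center and the other terms. ANCOVA at Visit 17 estimates all of those coefficients separately, which is why Equation 6.1 gains about 0.8% when the slopes are equal.

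**4. Only the baseline slope freed.** A separate simulation (1,500 trials per scenario, N = 530) compared Equation 6.1 with the same model plus a baseline-iGFR-by-visit term. The SE ratio was 1.000 with equal slopes. With a week-80 slope 0.075 to 0.225 higher, the term lowered the Visit 17 SE by about 0.5% to 6%. The formula puts the same interval at 0.6% to 5.0%, so the upper end is approximate.

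**5. Dependence on the assumed covariance.** With no extra covariates and slopes 0.90 / 0.79 / 0.775, the simulated ratio to ANCOVA was 1.019 under the covariance above. It was 1.006 with equal SDs of 10.1 and correlations 0.5, 0.5 and 0.8, where Visit 11 takes only 0.44 of the weight.

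**6. Power.** Planned scenario: 240 × 0.85 = 204 per arm, effect 3 × 0.94 = 2.82, SE = 10.1 × √(2/204) = 1.000. Power = Φ(2.82 − 1.96) = 0.805. With the SE 6% larger: Φ(2.82/1.06 − 1.96) = Φ(0.70) = 0.758. With it 0.5% larger: Φ(2.82/1.005 − 1.96) = Φ(0.846) = 0.801.

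**7. The ANCOVA equality.** In one simulated complete-data trial, the Visit 17 estimates were:

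- ANCOVA: 0.363
- every covariate by visit: 0.363
- Equation 6.1: 0.522
- baseline iGFR by visit, AER common: 0.495
- protocol model, AER common: 0.476
- protocol model, AER by visit: 0.363

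Equality needs every covariate to interact with visit.

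**The case against.** Common covariate coefficients with an unstructured covariance are a legitimate, parsimonious choice. SAP 6.6.2 already specifies ANCOVA at Visit 17 with the same covariates, SAP 6.9 requires checks of model assumptions, and the imputation model in SAP 6.5 does not carry the constraint. No document gives visit-specific slopes, so the size of any loss is assumed, and with equal slopes there is none.

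Most of this stands. It rules out three stronger readings that a reader might infer.

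- That Equation 6.1 breaks a promise of equality with ANCOVA. That statement is in Protocol 11.3, about a model which SAP 3.2 openly replaces. SAP 6.6.1 does not repeat it, the copy in the SAP appendix is for reference, and the protocol model as listed fails it too unless AER also varies by visit.
- That precision is lost as a matter of course. The loss depends on slopes that nobody has reported, and the constraint is neutral or slightly helpful when they are equal.
- That the primary estimate is biased. In the simulations the mean difference between the Equation 6.1 and ANCOVA estimates was about zero.

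What does not stand is that the point is already covered. A secondary ANCOVA leaves the standard error and p-value of the primary test unchanged. SAP 6.9 names no response to a baseline slope that varies by visit.

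**Conclusion.** The constraint is real and follows directly from the equation and its table. Its cost is conditional: about 0% of the Visit 17 standard error if the baseline slope is the same at all visits, and roughly 0.5% to 6% if the week-80 slope is 0.075 to 0.225 above the week-164 slope. The formula depends on g², so a gap in the other direction counts equally.

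The size rests on the assumed slopes, on residual SDs and correlations that place most of the weight on Visit 11, and on a baseline SD of 15.97 inferred from Protocol 11.10. It is for complete data; between-imputation variance was not modeled and would dilute the relative difference. No validity problem is shown. This is a free improvement.

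**What to change.** In Equations 6.1 and 6.2, take baseline iGFR out of the common covariate vector and give it a visit-indexed coefficient (a term γ_t × baseline iGFR). Relabel it as visit-specific in the two model tables. With three visits this adds 3 − 1 = 2 fixed effects, with N = 530. The Visit 16 analysis in SAP 6.7.1 uses the same fit and follows automatically.

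Visit-by-log10 AER, HbA1c and sUA terms are optional: 3 × 2 = 6 further fixed effects, 8 in all.

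Add one sentence to SAP 3.2 saying that the equality with ANCOVA in Protocol 11.3 is not claimed for Equation 6.1. Neither set of interactions above restores it, since center and albuminuria status would remain common. Interacting every covariate would restore it, but on complete imputed data the primary model would then coincide with the SAP 6.6.2 ANCOVA run on the same imputations, making that analysis redundant.

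The cost is SAP wording and a small code change, made before database lock and unblinding. No data collection changes.
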